## **9 Study Management**

### **9.1 Pre-study Documentation**

This study will be conducted in accordance with the ethical principles that have their origin in the Declaration of Helsinki as stated in 21 CFR §312.120(c)(4); consistent with GCP and all applicable regulatory requirements.

Before initiating this trial, the PI will have written and dated approval from the Institutional Review Board for the protocol, written informed consent form, subject recruitment materials, and any other written information to be provided to participants before any protocol-related procedures are performed on any participants.

The clinical investigation will not begin until either FDA has determined that the study under the Investigational Drug Application (IND) is allowed to proceed or the FDA has determined that the study is exempt from IND requirements.

The PI must comply with the applicable regulations in Title 21 of the Code of Federal Regulations (21 CFR §50, §54, and §312), GCP/ICH guidelines, and all applicable regulatory requirements. The IRB must comply with the regulations in 21 CFR §56 and applicable regulatory requirements.

### **9.2 Institutional Review Board Approval**

The protocol, the proposed informed consent form, and all forms of participant-facing materials related to the study (e.g., advertisements used to recruit participants) will be reviewed and approved by the UCSF IRB. Prior to obtaining IRB approval, the protocol must be approved by the Helen Diller Family Comprehensive Cancer Center Site Committee and by the Protocol Review Committee (PRC). The initial protocol and all protocol amendments must be approved by the IRB prior to implementation.

### **9.3 Informed Consent**

All participants must be provided a consent form describing the study with sufficient information for each participant to make an informed decision regarding their participation. Participants must sign the IRB-approved informed consent form prior to participation in any study-specific procedure. The participant must receive a copy of the signed and dated consent document. The original signed copy of the consent document must be retained in the medical record or research file.

## 9.4 Changes in the Protocol

Once the protocol has been approved by the UCSF IRB, any changes to the protocol must be documented in the form of an amendment. The amendment must be signed by the PI and approved by PRC and the IRB prior to implementation.

If it becomes necessary to alter the protocol to eliminate an immediate hazard to participants, an amendment may be implemented prior to IRB approval. In this circumstance, however, the PI must then notify the IRB according to institutional requirements.

## 9.5 Handling and Documentation of Clinical Supplies

The PI will maintain complete records showing the receipt, dispensation, return, or other disposition of all investigational drugs at the site. The date, quantity, and batch or code number of the drug, and the identification of participants to whom the investigational product has been dispensed by participant number and initials will be included.

The PI shall not make the investigational drug available to any individuals other than to qualified study participants. Furthermore, the PI will not allow the investigational product to be used in any manner other than that specified in this protocol.

## 9.6 Case Report Forms (CRFs)

The PI and/or designee will prepare and maintain adequate and accurate participant case histories with observations and data pertinent to the study. Study-specific Case Report Forms (CRFs) will document safety and treatment outcomes for safety monitoring and data analysis. All study data will be entered into OnCore® via standardized CRFs in accordance with the CTMS study calendar, using single data entry with a secure access account. Study personnel will complete the CRFs; the PI will review and approve the completed CRFs.

The information collected on CRFs shall be identical to that appearing in original source documents. Source documents will be found in the participant's medical records maintained by study personnel. All source documentation should be kept in separate research files for each participant.

In accordance with federal regulations, the PI is responsible for the accuracy and authenticity of all clinical and laboratory data entered onto CRFs. The PI will approve all completed CRFs to attest that the information contained on the CRFs is true and accurate.

The PI will be responsible for ensuring the accurate capture of study data. At study completion, when the CRFs have been declared to be complete and accurate, the database will be locked. Any changes to the data entered into the CRFs after that time can only be made by joint written agreement among the PI and the trial statistician.

All source documentation and CTMS data will be available for review/monitoring by the UCSF DSMC and regulatory agencies.

## 9.7 Oversight and Monitoring Plan

The UCSF Helen Diller Family Comprehensive Cancer Center DSMC will be the monitoring entity for this study. The UCSF DSMC will monitor the study in accordance with the NCI-approved Data and Safety Monitoring Plan (DSMP). The DSMC will routinely review all adverse events and suspected adverse reactions considered "serious." The DSMC will audit study-related activities to ensure that the study is conducted in accordance with the protocol, local

standard operating procedures, FDA regulations, and Good Clinical Practice (GCP). Significant results of the DSMC audit will be communicated to the IRB and the appropriate regulatory authorities at the time of continuing review, or in an expedited fashion, as applicable. See Appendix 2 - Data and Safety Monitoring Plan.

## **9.8 Record Keeping and Record Retention**

The PI is required to maintain adequate records of the disposition of the drug, including dates, quantity, and use by subjects, as well as written records of the disposition of the drug when the study ends.

The PI is required to prepare and maintain adequate and accurate case histories that record all observations and other data pertinent to the investigation on each individual administered the investigational drug or employed as a control in the investigation. Case histories include the case report forms and supporting data including, for example, signed and dated consent forms and medical records including, for example, progress notes of the physician, the individual's hospital chart(s), and the nurses' notes. The case history for each individual shall document that informed consent was obtained prior to participation in the study.

Study documentation includes all CRFs, data correction forms or queries, source documents, Sponsor-Investigator correspondence, monitoring logs/letters, and regulatory documents (e.g., protocol and amendments, IRB correspondence and approval, signed participant consent forms).

Source documents include all recordings of observations or notations of clinical activities and all reports and records necessary for the evaluation and reconstruction of the clinical research study.

In accordance with FDA regulations, the PI shall retain records for a period of 2 years following the date a marketing application is approved for the drug for the indication for which it is being investigated; or, if no application is to be filed or if the application is not approved for such indication, until 2 years after the investigation is discontinued and FDA is notified.

**Appendix 1 Performance Status Criteria**

ECOG Performance Status Scale		Karnofsky Performance Scale	
Grade	Descriptions	Percent	Description
0	Normal activity Fully active, able to carry on all pre-disease performance without restriction	100	Normal, no complaints, no evidence of disease
		90	Able to carry on normal activity; minor signs or symptoms of disease
1	Symptoms, but ambulatory Restricted in physically strenuous activity, but ambulatory and able to carry out work of a light or sedentary nature (e.g., light housework, office work)	80	Normal activity with effort; some signs or symptoms of disease
		70	Cares for self, unable to carry on normal activity or to do active work
2	In bed < 50% of the time Ambulatory and capable of all self-care, but unable to carry out any work activities Up and about more than 50% of waking hours	60	Requires occasional assistance, but is able to care for most of his/her needs
		50	Requires considerable assistance and frequent medical care
3	In bed > 50% of the time Capable of only limited self-care, confined to bed or chair more than 50% of waking hours	40	Disabled, requires special care and assistance
		30	Severely disabled, hospitalization indicated Death not imminent
4	100% bedridden Completely disabled Cannot carry on any self-care Totally confined to bed or chair	20	Very sick, hospitalization indicated Death not imminent
		10	Moribund, fatal processes progressing rapidly
5	Dead	0	Dead

## Appendix 2 Data and Safety Monitoring Plan for a Phase II or III Institutional Study

---

### Data and Safety Monitoring Plan for a Phase II or III Institutional Trial

#### 1. Oversight and Monitoring Plan

The UCSF Helen Diller Family Comprehensive Cancer Center (HDFCCC) Data and Safety Monitoring Committee (DSMC) is responsible for auditing data quality and participant safety for all HDFCCC institutional clinical trials. A summary of DSMC activities for this trial includes:

- Semiannual auditing (depending on trial accrual)
- Review of serious adverse events
- Minimum of biennial regulatory auditing

#### 2. Monitoring and Reporting Guidelines

Investigators will conduct a continuous review of data and participant safety at monthly site committee meetings where the results of each participant's treatment are discussed and documented in the site committee minutes.

All institutional Phase II and III therapeutic trials are audited on a semiannual basis, with all data from twenty percent of the enrolled participants audited by the DSMC Monitor/Auditor. The assigned DSMC Monitor/Auditor will review no more than a total of 10 participant charts during the course of auditing this trial. DSMC Monitor/Auditors will send a follow-up report to the study team within 20 business days after the auditing visit is complete for the PI and the study team to resolve all action items from this report within 20 business days. An abbreviated regulatory review (i.e., reviewing protocol and consent versions, SAEs, PVs, DOA logs, 1572 forms, etc.) will occur at each participant monitoring review; however, a full regulatory review will occur on a biennially basis by the DSMC for regulatory compliance.

Auditing of all enrolled participants in these trials will be complete after 20% of enrolled participants have been audited through five cycles of treatment. However, regulatory reviews of the trial, safety reviews (i.e., Serious Adverse Event (SAE) reviews and Protocol Violation (PV) reviews), and audit/inspection preparation (as applicable) will continue until the trial is closed by the IRB.

#### 3. Review and Oversight Requirements

##### 3.1 Adverse Event Monitoring

All Grade 3-5 adverse events (AEs), whether or not considered to be expected or unexpected and whether or not considered to be associated with the use of the

investigational agent(s) or study procedure, will be entered into OnCore®, UCSF's Clinical Trial Management System.

Adverse events are graded according to the Common Terminology Criteria for Adverse Events (CTCAE) as developed and revised by the Common Therapy Evaluation Program (CTEP) of the National Cancer Institute. Adverse events are further given an assignment of attribution or relationship to investigational agent or study procedure. Attribution categories are:

- **Definite** – The adverse event is clearly related to the investigational agent(s) or study procedure.
- **Probable** – The adverse event is likely related to the investigational agent(s) or study procedure.
- **Possible** – The adverse event may be related to the investigational agent(s) or study procedure.
- **Unrelated** – the adverse event is clearly not related to the investigational agent(s) or study procedure.

All Grade 3-5 adverse events entered into OnCore® will be reviewed on a monthly basis at the Site Committee meetings. The Site Committee will review and discuss the selected toxicity, the toxicity grade, and attribution assignment.

### 3.2 Serious Adverse Event Reporting

By definition, an adverse event is defined as a serious adverse event (SAE) according to the following criteria:

- Death.
- Life-threatening (i.e., results in an immediate risk of death).
- Requires inpatient hospitalization or prolongation of existing hospitalization,
- Permanent or significant disability/incapacity
- Gives rise to a congenital anomaly/birth defect, or cancer, or any experience that suggests a significant hazard, contraindication, side effect, or precaution that may require medical or surgical intervention to prevent one of the outcomes listed above.
- Event occurring in a gene therapy study.
- Event that changes the risk/benefit ratio of a study.
- Any other event the Principal Investigator judges to be serious or which would suggest a significant hazard, contraindication, side effect, or precaution.

Serious adverse event reporting will be in accordance with all IRB regulations. For trials conducted under an investigational new drug (IND) application, the SAE will be reported in accordance with Code of Federal Regulation Title 21 Part 312.32 and will be reported on a Med Watch form.

UCSF IRB website for guidance in reporting serious adverse events:

<https://irb.ucsf.edu/adverse-event>

Med Watch forms and information:  
[www.fda.gov/medwatch/getforms.htm](http://www.fda.gov/medwatch/getforms.htm)

All serious adverse events are entered into OnCore®, as well as submitted to the IRB (per IRB guidelines). The SAEs are reviewed and monitored by the Data and Safety Monitoring Committee on an ongoing basis and discussed at DSMC meetings, which take place every six weeks. The date the SAE is sent to all required reporting agencies will be documented in OnCore®.

If the SAE involves a subject death, and is determined to be possibly, probably or definitely related to the investigational drug or any research related procedure, the event must be reported to the DSMC Chair (or Vice Chair) and DSMC Director within one business day.

### 1.3 Review of Adverse Event Rates

If an increase in the frequency of Grade 3 or 4 adverse events (above the rate reported in the Investigator Brochure or package insert) is noted in the study, the Principal Investigator will notify the DSMC via report at the time the increased rate is identified. The report will indicate if the incidence of adverse events observed in the study is above the range stated in the Investigator Brochure or package insert.

If at any time the Investigator voluntarily holds enrollment or stops the study due to safety issues, the DSMC Chair (or Vice Chair) and the DSMC Director must be notified within one business day and the IRB must be notified as per IRB reporting regulations.

### Appendix 3 Prohibited Medications List

---

Drug	Trade name (if applicable)
BCG (Intravesical or vaccine) - ok if on ARM B	Theracys. TICE-BCG
BuPROPion	Wellbutrin
Cladribine - ok if on ARM B	Mavenclad
Conivaptan	Vaprisol
Dacomitinib	Vizimpro
Deferiprone - ok if on ARM B	Ferriprox
Dexamethasone	Prozac
Fludrocortisone	
FLUoxetine	Prozac
Hydrocortisone (topical is okay)	Cortef
Idelalisib	Zydelig
PARoxetine	Paxil
Methylprednisolone	Medrol
Ospemifene	Osphena
Prednisone	Deltisone
Tipranavir	Aptivus
Triamcinolone (topical, inhaled is ok)	Kenalog

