### 1.2.4 Histone Deacetylases (HDAC) and their inhibitors

A promising new class of drugs showing activity in cancer is the histone deacetylase inhibitors (HDACi). While these agents may have single-agent activity in cancer, they may also sensitize certain cancers to other types of therapeutic agents or overcome resistance. Histone deacetylases (HDAC) function to modulate gene expression by the removal of acetyl groups from histones. The addition of acetyl groups to lysine residues on the N-terminal tail of histones by histone acetyltransferases (HAT) results in the weakening of the bond between histones and DNA.

In contrast, removal of acetyl groups by HDACs results in the condensation of the nucleosomes and has been correlated with gene silencing. HDACs can be divided into at least three different classes, I-III. Each class contains several members of structurally and functionally variable HDACs. Alterations in the regulatory function of HATs and HDACs have been associated with the development of certain cancers. For example, mutations in the HAT gene CBP have been correlated with the development of certain colorectal and gastric cancers, whereas altered HDAC function has been associated with the onset of acute promyelocytic leukemia (APL). There are several inhibitors of HDACs that show anti-cancer activity in vitro and in vivo. These include the short-chain fatty acids (sodium butyrate, valproic acid (VPA)), the hydroxamic acids (suberoylanilide hydroxamic acid (SAHA), trichostatin A), the cyclic tetrapeptides (depsipeptide (FK-228)) and the benzamides (MS-275). Vorinostat, FK-228, MS-275, and others are currently undergoing early clinical testing.

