## 3 Study Design

### 3.1 Characteristics

We propose a single site Phase II, two-arm, open-label unblinded, 65-patient trial in patients with hormone therapy-resistant breast cancer (HTR) to test the role of epigenetic priming in a biomarker enriched patient population in HTR breast cancer. The two arms include Arm A: pembrolizumab, vorinostat, and tamoxifen and Arm B pembrolizumab and tamoxifen.

Patients will be evaluated for response at 9 weeks ( $\pm 1$  week) by RECIST1.1 (using IR-RECIST) and will continue on therapy if they have stable disease or response at the time of disease evaluations. Patients with progression on imaging but are clinically stable, may stay on study but will require follow-up staging after 4-6 weeks. Patients will be assessed continually for safety and tolerability as well as for any adverse events. If progression on therapy with pembrolizumab, patient may continue if clinically indicated and be re-evaluated after 4-8 weeks.

We will follow AEs of clinical interest as defined by Merck and will dose modify pembrolizumab as per Merck guidelines. We have significant prior experience with vorinostat, tamoxifen, and pembrolizumab combination and are facile with managing drug toxicities.

Tissue biopsies of all patients will be collected prior to enrollment to assess for pre-treatment of our immune signature and PD-L-1 expression. Follow up biopsies and peripheral blood collection will be taken from all patients post-treatment at 8-10 weeks to characterize changes in local tissue effects and antigen-specific cellular and humoral immune responses in peripheral blood.

Patients will be stratified by prior number of hormonal and chemotherapies.

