### 3.3.2 Exclusion Criteria

1. Prior treatment with pembrolizumab or other PD-(L)1
2. Any significant medical condition, laboratory abnormalities, which places the subject at unacceptable risk if he/she were to participate in the study.
3. Has a history of (non-infectious) pneumonitis/interstitial lung disease that required steroids or current pneumonitis/ interstitial lung disease.
4. Has known active Hepatitis B (e.g., HBsAg reactive) or Hepatitis C (e.g., HCV RNA [qualitative] is detected)"
5. Has a history of HBV
6. Has a history or current evidence of any condition, therapy, or laboratory abnormality that might confound the results of the study, interfere with the subject's participation for the full duration of the study, or is not in the best interest of the subject to participate, in the opinion of the treating investigator
7. Symptomatic central nervous system metastases. Subjects with brain metastases that have been previously treated and are stable for 6 weeks are allowed.
8. Persistent diarrhea or malabsorption  $\geq$  NCI CTCAE grade 2, despite medical management.
9. Unstable angina, significant cardiac arrhythmia, or New York Heart Association (NYHA) class 3 or 4 congestive heart failure.
10. Prior systemic cancer-directed treatments or investigational modalities  $\leq$  5 half-lives or 4 weeks, whichever is shorter, prior to starting study drug or who have not recovered from side effects of such therapy (except alopecia).
11. Active autoimmune disease except for vitiligo or hypothyroidism
12. Active and ongoing steroid use, except for non-systemically absorbed treatments (such as inhaled or topical steroid therapy for asthma, COPD, allergic rhinitis).
13. Major surgery  $\leq$  2 weeks prior to starting a study drug or who have not recovered from side effects of such therapy.
14. Pregnant or breastfeeding.
15. Known Human Immunodeficiency Virus (HIV) infection
16. Known history of tuberculosis
17. Known allergic reaction or intolerability to tamoxifen
18. Patients with prior history of DVTs must be on therapeutic or preventive anticoagulation

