## **6.6 Prohibited Medications**

Subjects are prohibited from receiving the following therapies during the Screening and Treatment Phase (including retreatment for post-complete response relapse) of this trial:

- Anti-cancer systemic chemotherapy or biological therapy
- Immunotherapy not specified in this protocol
- Chemotherapy not specified in this protocol
- Investigational agents other than Pembrolizumab
- Radiation therapy

- Note: Radiation therapy to a symptomatic solitary lesion or the brain may be allowed after consultation with the study PI and Merck.
- Live vaccines within 30 days prior to the first dose of trial treatment and while participating in the trial. Examples of live vaccines include, but are not limited to, the following: measles, mumps, rubella, chicken pox, yellow fever, rabies, BCG, and typhoid (oral) vaccine. Seasonal influenza vaccines for injection are generally killed virus vaccines and are allowed; however, intranasal influenza vaccines (e.g., Flu-Mist®) are live attenuated vaccines and are not allowed.
- Glucocorticoids for any purpose other than to modulate symptoms from an event of clinical interest of suspected immunologic etiology. The use of physiologic doses of corticosteroids may be approved after consultation with the study PI and Merck.

Subjects who, in the assessment by the investigator, require the use of any of the aforementioned treatments for clinical management should be removed from the trial. Subjects may receive other medications that the investigator deems to be medically necessary.

The Exclusion Criteria describes other medications, which are prohibited in this trial.

There are no prohibited therapies during the Post-Treatment Follow-up Phase.

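### Appendix 3 marks BCG as acceptable in Arm B, while Section 6.6 prohibits BCG vaccine for every subject; the two must be reconciled.

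*Combined protocol and SAP*

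**What the plan says.** Section 6.6 opens with a rule for the whole trial: "Subjects are prohibited from receiving the following therapies during the Screening and Treatment Phase". One item on its list is "Live vaccines within 30 days prior to the first dose of trial treatment and while participating in the trial". The examples given for that item are "measles, mumps, rubella, chicken pox, yellow fever, rabies, BCG, and typhoid (oral) vaccine". No item in Section 6.6 is qualified by treatment arm. The section closes by lifting all prohibitions in post-treatment follow-up, which is a distinction by phase and not by arm. It also says that a subject who needs one of the listed treatments should be removed from the trial.

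Appendix 3 is a drug-by-drug prohibited list. Its first entry is "BCG (Intravesical or vaccine) - ok if on ARM B". The same Arm B allowance is attached to two other entries, cladribine and deferiprone.

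Section 3.1 defines the arms as "Arm A: pembrolizumab, vorinostat, and tamoxifen and Arm B pembrolizumab and tamoxifen". Tables 5.2 and 5.3 give pembrolizumab at the same dose and on the same schedule in both.

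**The concern.** A prohibited-medication rule has to give one answer for a given patient. Here an Arm B patient who is offered BCG vaccine is barred by Section 6.6 and cleared by Appendix 3. Staff who check a prescription against the appendix would reach a different decision from staff who check it against the body.

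Two things are at stake. The first is safety: the product is one that the protocol itself classes as a live vaccine, and pembrolizumab is common to both arms, so the arm definitions do not explain why the rule should differ. The second is conduct: under Section 6.6 a patient who needs the product should leave the trial, while under Appendix 3 an Arm B patient could receive it and stay. The handling of otherwise similar patients could then depend on which page was consulted, and in one arm only.

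**Working it through.** No sample size, power or error rate enters this point, so there is nothing to recompute. The check is a side-by-side reading.

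1. **Scope of the prohibition.** Section 6.6 applies to all subjects in the screening and treatment phase. Its live-vaccine item runs from 30 days before the first dose and for as long as the subject is in the trial. Neither statement is limited to an arm.
2. **Is BCG covered?** Yes, as a vaccine: it is one of the named examples. Intravesical BCG is not mentioned anywhere in Section 6.6.
3. **What Appendix 3 says.** It covers both forms, vaccine and intravesical, and marks both as acceptable in Arm B.
4. **Comparison by arm and form.**
   - Arm A, vaccine: prohibited in both places. Consistent.
   - Arm B, vaccine: prohibited in Section 6.6, acceptable in Appendix 3. Direct contradiction.
   - Arm A, intravesical: prohibited in Appendix 3; Section 6.6 does not address the route.
   - Arm B, intravesical: acceptable in Appendix 3; Section 6.6 does not address the route. Ambiguous, but not an explicit conflict.
5. **Does treatment explain the difference?** By Section 3.1 and Tables 5.2 and 5.3, both arms get the same pembrolizumab regimen and the planned difference is vorinostat. The documents give no reason why BCG should be acceptable without vorinostat.
6. **Is the mismatch isolated?** No. Two further entries in Appendix 3 do not fit the body:
   - Dexamethasone is listed as prohibited, yet the gastrointestinal toxicity text in Section 5.2 includes it among allowed anti-emetics. Section 6.6 restricts glucocorticoids to suspected immune-related events of clinical interest, with physiologic doses subject to consultation, so Section 5.2 sits uneasily with that section too.
   - Prednisone is listed without qualification, yet Section 6.6 exempts glucocorticoids given for suspected immune-related events, and Table 5.4 names prednisone or an equivalent for several such events.
7. **Secondary item.** Section 1.2.4 names valproic acid among HDAC inhibitors. It does not appear in Appendix 3, Section 6.6 or the exclusion criteria, and Section 6.6 leaves other medically necessary drugs to the investigator. The only clause that could reach it is exclusion criterion 6, a discretionary bar at entry on therapy that might confound the results. Section 6.5.1 requires concomitant medication to be recorded from 28 days before the first dose to 30 days after the last, so use would be visible in the data.

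**The case against.** The strongest reply is that Section 6.6 binds every subject whatever an appendix says, so no one who reads the whole protocol would give BCG vaccine in Arm B. That is a fair account of how a careful reader might resolve the conflict, but the documents contain no statement that the body overrides the appendix. The appendix entry is specific and explicit, and it names the vaccine. The contradiction remains.

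A second reply is that the conflict is narrower than it looks, because Section 6.6 addresses BCG only as a vaccine. That stands, and the point is limited accordingly.

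Stronger readings are tempting on valproic acid. A reader might infer that the list opens Arm B to an HDAC inhibitor, that this would contaminate the comparator, and that one exposed patient could decide whether Arm B stops after its first stage. The documents do not support this. The silence applies to both arms and is an omission, not a permission. Exclusion criterion 6 and the concomitant-medication record cover part of it. No passage gives a frequency of valproic acid use in this population or shows that it would alter response to pembrolizumab. A reader might also want prior HDAC-inhibitor treatment excluded, as prior PD-(L)1 treatment is. Nothing in the plan requires that; it is an eligibility preference, and exclusion criterion 10 already imposes a washout on prior systemic cancer-directed and investigational treatment.

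**Conclusion.** The contradiction is established for BCG vaccine in Arm B: one place prohibits it and the other accepts it, under an identical pembrolizumab regimen. For intravesical BCG the finding is only that Section 6.6 is silent where Appendix 3 is not.

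A reader might infer that the appendix entry is simply an error. The documents do not settle that. They show that the two texts disagree, not which was intended.

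The effect on trial results cannot be quantified and is not claimed to be large, since no frequency of BCG use is given. The point matters because it concerns a safety rule that staff apply directly, and because the dexamethasone and prednisone entries show that Appendix 3 as a whole has not been aligned with the body. The valproic acid item is an optional clarification and carries no weight in this conclusion.

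**What to change.** - Reconcile the BCG entry in Appendix 3 with the live-vaccine item in Section 6.6, so that both state the same rule for each arm and for each form of BCG. Which rule is intended is for the sponsor to determine.
- In the same pass, check the remaining Appendix 3 entries against the body: the other two with an Arm B allowance, dexamethasone against Sections 5.2 and 6.6, and prednisone against Section 6.6 and Table 5.4.
- State which text governs if the appendix and the body differ.
- Optionally, add a sentence on how HDAC-inhibitor exposure outside the assigned regimen is handled in both arms. Recording is already provided for in Section 6.5.1.

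The cost is a text amendment through the approvals in Section 9.4. Reconciling the entries changes no endpoint, sample size or analysis.
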